Date: _____
<DD MMM YYYY>

Site: _____

ABBREVIATIONS

AAA	abdominal aortic aneurysm
ACT	Accelerating Clinical Trials
AE	adverse event
AHS	Alberta Health Services
AKI	acute kidney injury
Ca(+)	calcium
CI	confidence interval
CIHR	Canadian Institutes of Health Research
Co-PI	Co-Principal Investigator
CPG	Clinical Practice Guidelines
CRF	case report form
CRRT	continuous renal replacement therapy
CTCAE	Common Terminology Criteria for Adverse Events
CTO	Clinical Trials Office
CV	curriculum vitae
CVVH	continuous veno-venous hemofiltration
CVVHD	continuous veno-venous hemodialysis
CVVHDF	continuous veno-venous hemodiafiltration
DW	Dialyzing Wisely
eCRF	electronic case report form
EDC	electronic data capture
GCP	Good Clinical Practice
GI	gastrointestinal
HCO ₃ (-)	bicarbonate
HDRN	Human Data Research Network
Hgb	hemoglobin
hr	hour
ICH	International Council of Harmonization
ICU	intensive care unit
IRRT	intermittent renal replacement therapy
K(+)	potassium
KDIGO	Kidney Disease: Improving Global Outcomes
Kg	kilogram
MAKE	major adverse kidney event
MG(+)	magnesium
mL	millilitre
MOP	manual of procedures
MRP	most responsible physician
NAS	Nursing Activities Score
PI	Principal Investigator
PO ₄ (-)	phosphate
PROBE	prospective, randomized, open-label, blinded endpoint
PWLE	people with lived experience
RBC	red blood cells
RCT	randomized controlled trial

REB	research ethics board
REDCap	Research Electronic Data Capture
RRT	renal replacement therapy
SAE	serious adverse event
SC	steering committee
SD	standard deviation
SDM	surrogate decision-maker
SID	strong ion difference
SIV	site initiation visit
SOFA _{cv}	Sequential Organ Failure Assessment (cardiovascular)
SOP	standard operating procedure
TCPS2	Tri-Council Policy Statement on Ethical Conduct of Research Involving Humans – 2 (2022)
UF _{NET}	net ultrafiltration
VA/NIH	Veterans Affairs/National Institutes of Health
WCHRI	Women and Children's Health Research Institute

SUMMARY

Section	
Title:	LoW Dose-Intensity vs. Standard Dose-Intensity Continuous Renal Replacement Therapy in Critically Ill Patients (WISDOM): A Pilot Randomized Trial
Background:	An estimated 12-15% of critically ill patients receive RRT for acute kidney injury, the majority of whom initially receive continuous renal replacement therapy (CRRT). The 2012 Kidney Disease: Improving Global Outcomes (KDIGO) Clinical Practice Guidelines (CPG) for AKI recommend delivering a CRRT dose-intensity of 20-25 mL/kg/hr. This recommendation is derived from prior RCTs evaluating higher dose-intensity (35-40 mL/kg/hr vs. 20-25 mL/kg/hr) that have not shown any survival advantage. These findings translated to a dose-intensity of 20-25 mL/kg/hr becoming the de facto dose-intensity standard for patients receiving CRRT. In addition, because epidemiologic studies describing CRRT dose-intensity practices have consistently found that the “delivered” dose-intensity was often less than “prescribed” (only ~75-90%), usually due to therapy interruptions (i.e., circuit clotting; diagnostic imaging; minor surgical procedures), the 2012 KDIGO CPGs suggest that dose-intensity augmentation is required and that “ a higher prescription ” in the range of 25-30 mL/kg/hr is needed. The current practice, based on data from ICUs in Alberta, Canada and sites that participated in the international STARRT-AKI trial shows the range in median delivered CRRT dose-intensity is 26-30 mL/kg/hr. To date, no RCT has focused on evaluating or defining a minimally acceptable and safe CRRT dose-intensity threshold. Specifically, it is not clear whether a lower dose-intensity (10-15 mL/kg/hr) may be equally acceptable or even superior to the current guideline-directed standard (25-30 mL/kg/hr).
Objective:	The WISDOM research program aims to address whether a lower CRRT dose-intensity (10-15 mL/kg/hr) in critically ill patients with AKI is non-inferior for 90-day mortality compared to the current guideline-directed standard CRRT dose-intensity (25-30 mL/kg/hr) and will secondarily determine if lower CRRT dose-intensity can shorten RRT duration and improve kidney recovery versus the guideline-directed standard.
Study Design:	Multi-centre prospective, randomized, open-label, blinded endpoint (PROBE) pilot trial in adult ICU patients with AKI receiving CRRT.
Population:	ICU patients with AKI in whom the clinical team has decided to start CRRT or who are within 24 hours of having started CRRT will be potentially eligible. Each patient will fulfill all inclusion and have no exclusion criteria.
Eligibility:	Inclusion criteria:

	
i) age \geq 18 years, ii) patient weight \geq 55 kg iii) plan to initiate CRRT or within 24 hours of having started CRRT for acute kidney injury (AKI) iv) expected to survive and receive CRRT for a duration of \geq 48 hours v) able to consent or have an authorized representative consent after being informed on the details and risks of participation, unless a deferred consent process is approved by local REB.
 
Exclusion criteria: i) indication for sustained higher dose-intensity CRRT as designated by the attending clinician(s) ii) end-stage kidney disease receiving maintenance dialysis, iii) receipt of any RRT for AKI during the current hospitalization iv) inability to comply with the requirements of the study protocol.

Intervention:	
The experimental arm will be lower CRRT dose-intensity, defined as a delivered effluent flow rate of 10-15 mL/kg/hr. The rationale for this lower dose-intensity is based on the observed lower threshold of dose-intensity currently delivered in clinical practice and observational data showing that this threshold may be acceptable, tolerated and safe. The control arm will be guideline-directed standard CRRT dose-intensity, defined as delivered effluent flow rate of 25-30 mL/kg/hr. The standard dose-intensity is aligned with current practice and by recommendations from international CPGs.⁵ The current standard of care for CRRT dose-intensity provided in ICUs in Alberta and across the sites that participated in STARRT-AKI (39 Canadian sites) ranges between 26-30 mL/kg/hr. The CRRT dose calculation will use measured or estimated actual body weight, as previously described and recommended by CPGs. All enrolled patients will receive an active run-in period of standard dose-intensity of up to 24 hours (minimum 12 hours) to ensure initial metabolic and azotemic stabilization.

Outcomes:	
Primary Endpoint	
The primary feasibility endpoint is the difference (95% CI) in the total delivered effluent flow rate per patient between those in the lower and standard CRRT dose-intensity groups. The WISDOM pilot trial will target the detection of a minimum difference of 10 mL/kg/hr in average delivered dose-intensity between the groups.

Secondary Endpoints	
The secondary feasibility endpoints are: i) Ability to enroll an average of two patients per site per month. ii) Consent rate for participation by patient or surrogate decision-maker (SDM).

	
 iii) Time from eligibility (e.g., starting RRT) to randomization. iv) Protocol adherence for allocated CRRT dose-intensity. v) Ability to capture delivered CRRT dose-intensity measures. vi) Ability to capture patient and kidney endpoints at 90-days.
Biochemical Endpoints	
The secondary biochemical endpoints are:
 
 i) daily serum sodium, bicarbonate, base excess, strong ion difference (SID) and pH while receiving CRRT. ii) daily serum magnesium, potassium, and phosphate while receiving CRRT. iii) daily serum urea while receiving CRRT.
Process of Care Endpoints	
The process of care measures are:
 
 i) The lowest/highest CRRT dose-intensity delivered for any given hour following randomization. ii) The proportion of hours of CRRT when the dose-intensity is in the target range following randomization. iii) The total treatment time per day while receiving CRRT following randomization. iv) The number of hemofilter/circuit replacements while receiving CRRT following randomization. v) The total volume of replacement/dialysate fluid used per day following randomization. vi) The number and cumulative dose of supplementary electrolytes, protein and vitamins administered while receiving CRRT. vii) modified daily bedside (nursing) activity score, as a measure of nursing bedside workload, while receiving CRRT following randomization. viii) The mean daily net ultrafiltration (UF_{NET}) delivery while receiving CRRT following randomization.
Safety	
The safety endpoints are:
 
 i) occurrence of trial-related adverse and serious adverse events. ii) occurrence of adverse events and serious adverse events leading to discontinuation of the trial intervention.
Tertiary Endpoints	
The trial will measure and describe selected outcomes, including: duration of RRT; transition from CRRT to IRRT; receipt of RRT at hospital discharge, 30-days and 90-days; RRT-free days at 90-days; ICU mortality; hospital mortality; 90-day mortality; a composite of major adverse kidney events (MAKE) at 30-days and 90-days; change in estimated glomerular filtration rate (baseline to 90-days), daily receipt of non-renal organ support, ICU duration of stay, hospital duration of stay and re-hospitalization within 90-days.

Sample Size Estimation:	The sample size for the WISDOM pilot trial will address the detection of a minimum difference in the delivered dose-intensity of CRRT between the groups. Based on the ability to detect a minimum difference of 10 mL/kg/hr in dose-intensity, assuming the delivery of 25 mL/kg/hr in the standard dose-intensity group and 15 mL/kg/hr in the lower dose-intensity group, with a conservative standard deviation (SD) of 15, 90% power, and an alpha of 0.05, a total sample of 96 patients is needed (48 patients per group). This will be inflated to 100 patients to account for any withdrawal or dropout.
Registration:	Clinicaltrials.gov: NCT06446739 (June 6, 2024)

1. ADMINISTRATIVE INFORMATION

1.1 Lay Title

Low vs. Standard Dose-Intensity CRRT in Critically Ill Patients: A protocol for a pilot, randomized controlled trial comparing lower dose-intensity to standard dose-intensity continuous renal replacement therapy (CRRT) in adult patients in the intensive care unit (ICU).

1.2 Trial Registration

The trial is registered on ClinicalTrials.gov (<https://clinicaltrials.gov/>) – NCT06446739 (June 6, 2024).

1.3 Protocol Version

Version 2.0

1.4 Funding

ACT/HDRN (CIHR). Additional applications for funding are in progress.

1.5.2 Steering Committee

The Steering Committee is responsible for providing overall oversight of the WISDOM trial. Its membership includes the study co-chairs and other individuals with specialized knowledge in critical care and experience in running, and oversight of, clinical trials.

The Steering Committee will be accountable for the:

- Design and conduct of the study;
- Preparation of the essential study documents, including the protocol, protocol amendments, manuals and data collection forms;

- Review of data collection practices and procedures;
- Monitoring recruitment and retention of study participants;
- Modifications in study procedures, as appropriate;
- Allocation of resources based on priorities of competing study demands;
- Review of study progress in reaching goals and appropriate actions to ensuring the likelihood of achieving those goals.

A list of the Steering Committee members will be maintained in the Manual of Procedures and updated as needed.

1.5.5 Coordinating and data management centre

The Clinical Trials Office (CTO), Faculty of Medicine and Dentistry, University of Alberta will act as the coordinating and data management centre for this phase of the trial.

2. INTRODUCTION – THE NEED FOR A TRIAL

2.1 Background - what is the problem to be addressed?

Acutely ill patients admitted to the intensive care unit (ICU) are frequently exposed to a spectrum of risk factors for development of acute kidney injury (AKI).[1, 2] In those patients with more severe AKI characterized by azotemic, metabolic, acid-base and fluid complications that are generally refractory to medical therapy, renal replacement therapy (RRT) is often initiated.[3] An estimated 12-15% of critically ill patients receive RRT; however, this can exceed 20% in those with septic or cardiogenic shock.[1] Across high- and middle-income countries, most critically ill patients (>70%) will initially receive acute RRT in the form of continuous renal replacement therapy (CRRT).[4]

CRRT has several important aims in the context of AKI: i) achieve and maintain fluid, electrolyte, acid-base homeostasis; ii) achieve and maintain toxic/metabolic solute homeostasis; iii) facilitate life support interventions as indicated (e.g., nutrition, medications, transfusions); and iv) mitigate the hazards of severe complications attributable to AKI (i.e., hyperkalemia; acidemia, pulmonary edema).[5] RRT can also theoretically act as a broader platform to support multiple organs in critical illness, potentially mitigating the non-kidney organ dysfunction that may be exacerbated by severe persistent AKI and aid in facilitating weaning of organ support (e.g., invasive mechanical ventilation).[6]

To date, several aspects of acute RRT have been the focus of randomized controlled trials (RCTs), some having informed specific recommendations for acute RRT in the 2012 KDIGO clinical practice guidelines (CPGs) for AKI[7], and these include the optimal selection and timing of RRT initiation (early vs. delayed)[8-11], selection of RRT modality (continuous vs. intermittent)[12-14], regimens for anticoagulation (heparin vs. citrate)[15, 16], and delivered dose-intensity (standard vs. high-intensity).[17-22]

The 2012 KDIGO CPGs (Chapter 5.8) currently “recommend delivering an effluent volume of 20-25 mL/kg/hr for CRRT in AKI” (1A recommendation) and further suggest that “this will usually require a higher prescription of effluent volume” (not graded)[7]. Several small, single-center trials had variably suggested that higher dose-intensity of CRRT was associated with improved outcomes in critically ill patients with severe AKI.[19, 20, 22] In the landmark single centre RCT by Ronco and colleagues, survival at 15 days following CRRT discontinuation was compared among patients allocated to effluent flow rates of 20 mL/kg/hr, 35 mL/kg/hr and 45 mL/kg/hr, respectively.[22] Survival was found to be lowest among patients allocated to 20 mL/kg/hr. The publication of this RCT translated into widespread adoption of a minimum CRRT dose-intensity effluent rate of 35 mL/kg/hr.

However, this finding was not replicated in two large high-quality multicenter RCTs.[17, 18] In the VA/NIH ATN study, performed in centres in the US, CRRT was predominantly used in patients with hemodynamic instability.[18] Patients were randomized to pre-dilution continuous veno-venous hemo-diafiltration (CVVHDF) either dosed at an effluent flow rate of 20 mL/kg/hr in the lower dose-intensity arm or 35 mL/kg/hr in the higher dose-intensity arm. In the RENAL study, performed in centres across Australia and New Zealand, patients were randomized to CVVHDF either at an effluent flow rate of 25 mL/kg/hr in the less dose-intensive arm or 40 mL/kg/hr in the more dose-intensive arm.[17] In both dose-intensity groups, the delivered dose was split equally between dialysate and post-dilution hemofiltration. Neither study detected differences in survival or kidney recovery from the higher dose-intensity CRRT, including across several subgroup analyses (e.g., sepsis). Notably, both RCTs found that the delivered dose-intensity was often less than the prescribed dose-intensity. Based on the findings from these two rigorous RCTs, the 2012 KDIGO CPGs recommended a minimum CRRT dose-intensity of 20-25 mL/kg/hr.[7] Moreover, the finding that delivered dose-intensity was frequently below prescribed, contributed to further suggestions that careful attention should be given to ensuring that the target dose-intensity is monitored and actually delivered, while need to further augment the CRRT prescription to 25-30 mL/kg/hr is needed. This de facto threshold dose-intensity of 25-30 mL/kg/hr advocated by the KDIGO CPGs has not been the focus of rigorous evaluation in a RCT.[23]

2.2 Why is the trial needed now?

No RCT to date has specifically evaluated the lower dose-intensity threshold for critically ill patients receiving CRRT though two pilot trials are ongoing (Clinicaltrials.gov: NCT6021288 and NCT06014801).

Overall, there has been no specific evidence or guidance on the minimum dose-intensity targets for patients receiving CRRT. This is important for several reasons. First, CRRT is an invasive, resource intensive and expensive therapy.[6] As such, there should be a concerted effort to minimize time on RRT and facilitate early recovery and weaning. Second, abundant evidence derived from secondary analyses have suggested that higher CRRT dose-intensity can propagate oliguria, prolong the need for CRRT and disrupt and delay kidney recovery.[21, 24] This would imply that lower dose-intensity may facilitate kidney recovery and earlier weaning from RRT. Third, evidence has emerged that higher dose-intensity may have non-renal organ support implications, such as risk of cardiac arrhythmias and delayed weaning from invasive mechanical ventilation.[25] Fourth, evidence derived from observational registries has shown that lower CRRT dose-intensity (~10-18 mL/kg/hr), aligned with the lower CRRT dose-intensity proposed herein, can provide comparable efficacy for azotemic, metabolic and acid-base control.[26-28] Observational data have suggested a prescribed CRRT dose-intensity of 15 mL/kg/hr is not associated with worse outcomes compared with guideline directed dose-intensity.[27, 28] This is lower quality evidence, however, implies that lower dose-intensity may be acceptable and safe. Fifth, it is plausible that following a short period of metabolic stabilization with CRRT (~12-24 hours), the minimum CRRT dose-intensity threshold currently recommended is excessive and has the potential for unmeasurable harm (e.g., excess removal of electrolytes, micronutrients, and medications [antimicrobials; antiepileptics; etc.]). Patients receiving CRRT for sustained periods of time (>48 hours) routinely require supplementation to replace the loss of electrolytes, protein and vitamins. Finally, a lower CRRT dose-intensity may have a meaningful impact on reducing bedside nursing workload (e.g., fewer replacement solution bag changes; less need for supplementation); reducing avoidable waste (e.g., reduce carbon footprint) and reducing costs attributable to CRRT (e.g., reducing total volume of replacement/dialysate solutions; shortening total CRRT duration)..[29]

2.3 How will the results of this trial be used?

While this proposal outlines a pilot feasibility trial, it is aimed at performing a larger rigorous RCT that will generate generalizable and high-quality evidence to impact clinical practice. The findings of the main phase of the WISDOM trial program will provide clearer evidence to guide the prescription of a minimal dose-intensity for patients receiving CRRT. Current practice in Alberta for the prescription of CRRT is variable. Based on data from October 1, 2023 to December 31, 2023, there were 518 patients receiving CRRT

across Alberta (2,790 CRRT-days; average 5.4 days per patient) and an estimated 77% of these patients receiving CRRT fulfilled the criteria for AKI. Our team has implemented a provincial program, Dialyzing Wisely (DW), to monitor and report key performance and quality indicators of CRRT, aimed at implementing evidence-formed best practices and minimizing unnecessary variations in practice.[30] A key measure this program has implemented is the dose-intensity delivered to patients receiving CRRT. Currently estimates from this audit show a mean (SD) effluent rate of 27.7 mL/kg/hr (SD 15; min 11; max 91) for patients receiving CRRT. This would imply there are currently variations in practice and that a meaningful proportion of patients are receiving less than the current guideline directed recommended dose-intensity. The Dialyzing Wisely platform provides key infrastructure to implement, measure process and outcome data, and disseminate the findings from this trial. Moreover, the findings from this trial can be immediately implemented into clinical practice, including into provincial standardized CRRT order sets, and used to establish revised dose-intensity targets for reporting in the Dialyzing Wisely program. Furthermore, if the main phase trial establishes that lower dose-intensity is acceptable and safe with no clinically meaningful differences in patient-centred or health service outcomes, the lower dose-intensity would become the current default standard and inform clinical practice guidelines for CRRT management worldwide.

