3.5.2 Secondary Endpoints

The secondary feasibility endpoints are:

- i) Ability to enroll an average of 2 patients per site per month. We believe a target of 2 per month is feasible across sites in Alberta given the number of patients starting CRRT per month (~32 new CRRT initiations per month) and accrual at sites during the STARRT-AKI trial.
- ii) The ability to enroll >50% of fully eligible patients.
- iii) Time from eligibility (e.g., starting RRT) to randomization with a target of >75% of eligible patients within 12 hours.
- iv) Protocol adherence for allocated CRRT dose-intensity. We believe a target in-range dose-intensity of >80% to be adequate.
- v) Ability to capture delivered CRRT dose-intensity measures. This is a process measure of trial implementation and fidelity. We believe a target of electronic capturing >95% of daily time-averaged CRRT dose-intensity data to be adequate. This will enable an assessment of difference in CRRT dose-intensity between groups.
- vi) Ability to capture patient and kidney endpoints at 90-days from randomization. We believe a target of >95% ascertainment to be adequate.

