3.6 Sample size calculation and recruitment

For the WISDOM pilot trial, our primary sample size consideration will address the detection of a minimum difference in the delivered dose-intensity of CRRT between the groups. For the WISDOM pilot trial, we are targeting a total sample size of 100 patients (50 patients per group). This is based on the ability to detect a minimum difference of 10 mL/kg/hr in dose-intensity, assuming delivery of 25 mL/kg/hr in the standard dose-intensity group and 15 mL/kg/hr in the lower dose-intensity group, with a conservative standard deviation (SD) of 15, 90% power, and an alpha of 0.05. This would translate into a sample of 96 patients (48 patients per group) that will be inflated to 100 to account for any withdrawal or dropout (See Table below).

Table. Sample Size Calculation Estimates.

Scenario	Difference in Dose Intensity	Standard Deviation	Power	Estimated Sample (Total)
1	10	5.0	0.9	12
2	10	7.5	0.9	24
3	10	10.0	0.9	44
4	10	12.5	0.9	66
5	10	15.0	0.9	96
6 (ATN Trial)	15	6.3*	0.9	18
7 (RENAL Trial)	15	15.3**	0.9	100
* From the ATN trial, based on average standard deviation for both groups of the aggregate total effluent flow rate delivered.[18]				
** From the RENAL trial, based on average standard deviation for both groups of the aggregate total effluent flow rate delivered.[17]				

For the WISDOM pilot trial, the total sample of 100 patients would translate into a target recruitment of 4 patients per week (50% of expected eligible) across 5-10 sites, thereby requiring an estimated 6-10 months to complete, if all sites are active.

We will further explore the practicality of identification of eligible patients, site-specific recruitment, protocol adherence, and data monitoring and ascertainment, that will inform the logistical planning and operations of a larger-scale multi-centre trial.[34]

All patients enrolled in the trial will be admitted to and monitored in an ICU setting. The primary and secondary feasibility endpoints, along with biochemical and process of care endpoints will be captured in local hospital medical records (either paper charts or electronic medical records) and data repositories. Data will be captured electronically where feasible, otherwise, standardized paper case report forms will be used. The expected rate of loss to follow-up will be low for ICU and hospital-specific outcomes

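### As worded, the 12-hour randomisation benchmark cannot be met at the planned enrolment rate, and the Alberta CRRT counts in sections 2.3 and 3.5.2 differ about four- to five-fold

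*Protocol*

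**What the plan says.** **Timing and enrolment benchmarks.** Protocol section 3.5.2 lists secondary feasibility endpoints with numerical targets. Endpoint ii is "The ability to enroll >50% of fully eligible patients". Endpoint iii is "Time from eligibility (e.g., starting RRT) to randomization with a target of >75% of eligible patients within 12 hours". Section 3.6 plans a "target recruitment of 4 patients per week (50% of expected eligible) across 5-10 sites". The same section provides for a screening log in which patients who were eligible but not randomised are recorded as a group of their own.

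**Patient numbers.** Section 2.3 reports an Alberta audit: "Based on data from October 1, 2023 to December 31, 2023, there were 518 patients receiving CRRT" and, continuing, "across Alberta (2,790 CRRT-days; average 5.4 days per patient". It adds that "an estimated 77% of these patients receiving CRRT fulfilled the criteria for AKI". Endpoint i in section 3.5.2 is "Ability to enroll an average of 2 patients per site per month". It is called feasible for sites in Alberta "given the number of patients starting CRRT per month (~32 new CRRT initiations per month", together with accrual in an earlier trial.

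**The concern.** Endpoints ii and iii both refer to eligible patients but ask for incompatible fractions. A patient who is never randomised cannot be randomised within 12 hours, so the enrolment fraction caps endpoint iii. If the cap lies below the target, the benchmark measures enrolment and says nothing about speed.

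Separately, the two Alberta figures should describe the same flow of patients, yet one is several times the other. The smaller one is a stated reason for believing that two patients per site per month can be reached.

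The trial exists to establish feasibility (section 2.5), and section 7.9 makes expansion depend on it. A benchmark that fails by wording, or an accrual rationale that cannot be traced to a consistent count, weakens what the pilot can report on that question.

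**Working it through.** **A. The 12-hour benchmark**

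Let *e* be the fraction of eligible patients who are randomised and *q* the fraction of randomised patients who are randomised within 12 hours. The share of eligible patients randomised within 12 hours is *e* × *q*, which cannot exceed *e*. Endpoint iii needs *e* × *q* > 0.75, so *q* > 0.75 / *e*.

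| Enrolment fraction *e* | *q* must exceed | Possible? |
|---|---|---|
| 0.50 (plan, section 3.6) | 1.50 | no |
| 0.60 | 1.25 | no |
| 0.75 | 1.00 | no |
| 0.80 | 0.94 | yes |
| 0.90 | 0.83 | yes |
| 1.00 | 0.75 | yes |

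Every enrolment fraction above 50% and up to 75% therefore passes endpoint ii and must fail endpoint iii. At the planned 50%, a trial that randomised every enrolled patient within 12 hours would score 50% on the written denominator and 100% with randomised patients as denominator.

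The start of the clock is also incomplete. Inclusion criterion iii (section 3.3.1) admits patients for whom CRRT is only planned, whereas endpoint iii gives the start of RRT as its example of eligibility. A patient randomised before CRRT starts has no defined time.

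**B. The Alberta counts**

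Inputs from section 2.3: 518 patients, 2,790 CRRT-days, 77% with AKI, 1 October to 31 December 2023 (3 months, 92 days). Input from section 3.5.2 i: about 32 initiations a month.

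1. Internal check of the audit: 2,790 / 518 = 5.39 days, which reproduces the stated 5.4. The patient and day counts agree with each other.
2. All CRRT patients: 518 / 3 = 172.7 a month; 172.7 / 32 = 5.4.
3. AKI only: 172.7 × 0.77 = 133.0 a month; 133.0 / 32 = 4.2.
4. New starts only: 2,790 / 92 = 30.3 patients on CRRT on an average day. Removing that many as already on treatment when the window opened gives (518 − 30.3) / 3 = 162.6 a month; 162.6 / 32 = 5.1.
5. Both restrictions together: 162.6 × 0.77 = 125.2 a month; 125.2 / 32 = 3.9.
6. Reverse check: 32 a month is 96 a quarter. Then 2,790 CRRT-days would mean 2,790 / 96 = 29.1 days per patient, against the stated 5.4.
7. Assumption, not in the document: if 518 were a 12-month count, 518 / 12 = 43.2 a month, and × 0.77 = 33.2 with AKI. The second figure is close to 32.

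**C. The eligible number implied by section 3.6**

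4 a week / 0.50 = 8 eligible a week, or 8 × 52.18 / 12 = 34.8 a month. On the dated audit, AKI patients number 518 × 0.77 / (92 / 7) = 30.3 a week, so 8 a week would be 26% of them.

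The stated duration holds together without the audit. 100 patients at 4 a week (17.4 a month) take 5.7 months, and 2 per site per month at 5 to 10 sites takes 10 to 5 months, against the stated 6 to 10.

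**The case against.** **On the 12-hour target.** More than 50% is a floor, so the trial may enrol more. A time to randomisation exists only for randomised patients, so a sensible reader would use them as denominator, and the target is then attainable. Both points stand, and for that reason the benchmark should not be called unattainable outright. But section 3.6 plans 50%, and the protocol itself treats eligible patients who were not randomised as a recorded group, so the literal reading is not strained. Someone assessing the endpoint as written would have to score it as failed.

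**On the patient counts.** The 32 might refer only to participating Alberta sites. That is possible, but the text names no subset.

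**Stronger readings that the document does not support.**
- A reader might infer that the 8 eligible patients a week implied by section 3.6 contradicts the audit. The current text does not derive that figure from the 518; a sentence doing so appears only in the amendment history. Current section 3.2 places sites across Canada and internationally. The other eligibility criteria (weight, expected CRRT of at least 48 hours, no earlier RRT in the hospitalisation, clinician exclusion) and the limit of 5 to 10 sites could reduce 30.3 a week to 8. The figure is unexplained, not contradicted.
- A reader might infer that 4 a week is only 13% of the available patients (4 / 30.3) and that the enrolment-fraction benchmark must fail. Patients with AKI on CRRT are not the same as fully eligible patients, which is the denominator of endpoint ii, so this does not follow.
- A reader might take the near match at step B7 as proof that the audit covered 12 months. The match appears only after the 77% AKI restriction, which section 3.5.2 i does not mention. It is a lead to check, no more.

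**Conclusion.** Both parts hold, within limits.

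Endpoint iii is wrongly specified as written: a trial that recruits exactly to plan misses it by construction. This rests on reading the word eligible literally and on enrolment of 75% or less.

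The 518 patients in one quarter and the roughly 32 initiations a month cannot both describe Alberta as stated. The mismatch is about four- to five-fold (3.9 to 5.4 depending on who is counted). The document does not show which figure is wrong, or whether the smaller one covers fewer sites, so the direction of any correction to the accrual rationale is unknown.

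The consequence is confined to the 12-hour benchmark and to the justification of the per-site accrual target. The sample size of 96 inflated to 100, the primary endpoint, and the benchmark of enrolling more than 50% of fully eligible patients do not depend on either point.

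**What to change.** 1. Reword endpoint iii in section 3.5.2 as more than 75% of randomised patients being randomised within 12 hours of CRRT start. State how patients randomised before CRRT start are counted, for example as zero hours or as a separately reported group.
2. Re-run the audit query behind section 2.3 and confirm the period and the count. If both are right, name the sites or the definition that yields about 32 initiations a month.
3. Restate the justification in section 3.5.2 i from the verified figure, and add to section 3.6 the basis of the expected eligible number: which sites, which eligibility criteria, what yield.

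The cost is one data check and a few edited sentences, handled as an amendment or administrative update with the ethics review that section 7.2 requires. The design, sample size and data collection stay as they are. The accrual justification may read more or less favourably once the base is verified.
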